# 6.10. Efficacy Analyses

The analysis of the viral load lab results will utilize the following conventions:

For qualitative endpoints in the trial (viral clearance yes/no, time to viral clearance) the lab determination of "positive"/ "negative" will be used. SARS-CoV-2 clearance (yes/no) is defined as 2 consecutive negative tests for the SARS-CoV-2 virus. The date of viral clearance is defined as the earliest date of the 2 consecutive negative tests.

For quantitative endpoints in the trial (change from baseline, area under the response viral load curve [AUC]), the viral load will be derived based on cycle threshold (Ct) values with the following considerations:

Two Ct values will be provided on 2 different genes: N1 and N2. N1 will be used as the primary measure; N2 will only be used when the Ct value for N1 is not available.
Ct values range between 0 and 45.
Negative CoV-2 tests will be associated with a Ct value of 45.
The (log base 10) viral load will be calculated from the Ct value (45-Ct)/log 10, or (45-Ct)/3.321928.

□ A normalization step will also be applied. The viral load Ct value described in the previous steps will be subtracted by (RP Ct – 26.17), where RP Ct is a measure for the amount of material in the sample and 26.17 is a historical average value of RP Ct for this assay, used here to center the RP Ct values.

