### 6.16.2.6. Viral Load Plots

The 7th octile (87.5th percentile) for the observed viral load data will be plotted across Day 1, Day 5, Day 7, and Day 11. Additionally, the 4th (median), 5th (62.5th percentile), and 6th (75th percentile) octiles will be plotted separately.

The 4th, 5th, 6th, and 7th octile for viral load data adjusted for days from symptom onset at baseline will be plotted across Day 1, Day 5, Day 7, and Day 11. Viral load participant data will be adjusted by multiplying the participants number of days from symptom onset at baseline by 0.158 (estimated mean daily decrease in viral load) and then adding the result to all of the participants non-zero viral load measurements. Note, that if the observed viral load is zero, it will not be adjusted.

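### RP normalization in SAP 6.10 is not limited to positive tests, so a virus-negative swab is given a non-zero viral load

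*SAP*

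**What the plan says.** SAP 6.10 lists the conventions for the quantitative viral load endpoints.

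- Range: "Ct values range between 0 and 45".
- Negatives: "Negative CoV-2 tests will be associated with a Ct value of 45".
- Conversion: "The (log base 10) viral load will be calculated from the Ct value (45-Ct)/log 10, or (45-Ct)/3.321928".
- Normalization: "The viral load Ct value described in the previous steps will be subtracted by" (RP Ct − 26.17). RP Ct measures how much material the sample holds, and "26.17 is a historical average value of RP Ct for this assay, used here to center the RP Ct values".

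No exemption for negative tests is stated, nor any cap or floor after normalization. Clearance (yes/no and time to) is handled separately, from the laboratory's positive or negative call.

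Three later sections matter. SAP 6.16.1.1 analyses change from baseline at Days 5, 7 and 11 by MMRM, and computes viral AUC only from measured values above the lower limit of quantification (LLOQ). SAP 6.16.2.6 plots octiles of viral load at Days 1, 5, 7 and 11. In one version of those plots it adds 0.158 times the days since symptom onset to non-zero values, with the exception: "Note, that if the observed viral load is zero, it will not be adjusted".

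**The concern.** Ct 45 gives a negative test a log10 load of 0. The normalization step then acts on the Ct from the steps before it, and those steps include the 45 given to negatives. Correcting for sample material makes sense when virus was detected. When none was detected, the only quantity left in the result is the RP term. A negative swab with little material (high RP Ct) then shows virus, and one with much material shows a load below zero.

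This also conflicts with two of the SAP's own statements. A load below zero implies a Ct above 45, outside the stated range. And the zero exception in 6.16.2.6 presumes that exact zeros exist. If it is applied to normalized values it would almost never operate, and negatives would also receive the onset adjustment.

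**Working it through.** **Inputs.** Ct for a negative = 45; divisor = 3.321928; centring value = 26.17 (all SAP 6.10). Daily decline = 0.158 (SAP 6.16.2.6). The RP Ct of individual samples is not in the documents; 26.17 ± 4 cycles is assumed below.

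**Check of the plan's own figure.** log2(10) = 3.321928, so the divisor is right for converting cycles to log10. Before normalization a negative gives (45 − 45)/3.321928 = 0.

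**Rule as written, for a negative test.**

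Normalized Ct = 45 − (RP Ct − 26.17)

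log10 load = (45 − normalized Ct)/3.321928 = (RP Ct − 26.17)/3.321928

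| RP Ct (assumed) | Normalized Ct | log10 load of a negative |
|---|---|---|
| 22.17 | 49 | −1.204 |
| 24.17 | 47 | −0.602 |
| 25.17 | 46 | −0.301 |
| 26.17 | 45 | 0 |
| 27.17 | 44 | +0.301 |
| 28.17 | 43 | +0.602 |
| 30.17 | 41 | +1.204 |

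**Per cycle, without assuming any range.** 1/3.321928 = 0.301 log10, and 0.301/0.158 = 1.9 days of decline.

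**Change from baseline, one example.** Take a baseline Ct of 25 with RP Ct 26.17, so baseline load = (45 − 25)/3.321928 = 6.021. If the next swab is negative and counts as zero, the change is −6.021. As written, it runs from −1.204 − 6.021 = −7.225 (RP Ct 22.17) to +1.204 − 6.021 = −4.816 after rounding (RP Ct 30.17).

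**Other readings of the text.**

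- Capping normalized Ct at 45 removes the values below zero, but leaves the positive ones for RP Ct above 26.17.
- Subtracting the RP term from the log10 load instead gives 26.17 − RP Ct, for example +2 at 24.17 and −2 at 28.17.

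Neither returns every negative to zero.

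**Effect on a visit mean.** If a share p of swabs at a visit is negative, their contribution to the error in the raw mean is p × (mean RP Ct of those swabs − 26.17)/3.321928. It vanishes when their mean RP Ct is 26.17, and what remains is extra variance. Upper octiles do not have this protection: spreading a cluster of zeros to both sides moves percentiles above the middle of that cluster upwards, even when the average shift is nil.

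**The case against.** A reader might infer more than the documents support.

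- **That viral AUC, and viral load out to Day 29, would mostly measure swab adequacy.** SAP 6.16.1.1 restricts both AUCs to measured values above the LLOQ, and a negative would not ordinarily qualify. Of these analyses, only AUC(0-D29) runs past Day 11. The protection is not complete, because no LLOQ value is given and the SAP does not say whether the limit applies before or after normalization.
- **That estimates are biased, with poor swabs from small children passing for residual virus.** The documents give no rate of negative swabs by day, no RP Ct distribution and no evidence on swab quality by age. As 26.17 is a historical average, the shifts may largely cancel in means.
- **That the authors meant to normalize negatives.** The zero exception in 6.16.2.6 suggests the opposite, and it may refer to values before normalization. The 0 to 45 range, if kept after normalization, would remove the below-zero half.

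These points narrow the scope and suggest an exemption that was intended but not written. They do not change what 6.10 instructs a programmer to do, and no reading tried sets all negatives to zero. The case for low priority is also fair: viral load is exploratory, the cohort is single-arm, and efficacy is to be extrapolated from adults.

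**Conclusion.** The point holds for a limited set of analyses. As written, SAP 6.10 gives a negative swab a log10 load of (RP Ct − 26.17)/3.321928: 0.301 log10 per RP cycle, and about −1.2 to +1.2 if RP Ct varies by ±4 cycles. The formula rests on the SAP alone; the range is an assumption.

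The exposure is the change-from-baseline MMRM at Days 5, 7 and 11 and the octile plots in 6.16.2.6. The Day 7 PHVL analysis in 6.3.5 is also exposed if it uses the derived load. The consequences are added noise, distorted upper octiles, and a zero exception that almost never applies if it uses normalized values. Bias in means requires the cohort's mean RP Ct (strictly, that of the negative swabs at the visit) to differ from 26.17, which the documents do not show. The PK primary endpoint, safety and clearance are unaffected. It should be corrected before the viral load analyses are programmed, but it does not threaten the study's main conclusions.

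**What to change.** State in SAP 6.10 that RP normalization applies to positive tests only and that negative tests keep log10 viral load 0. The zero exception in 6.16.2.6 then works as it appears to have been intended. It would help to say in 6.16.1.1 what the LLOQ is and whether it applies before or after normalization.

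The cost of the main change is one SAP sentence and one line of code, with no new data. There is a small downside. A negative from a swab with little material counts as zero load, and there is a step between negatives and weak positives: at RP Ct 30, a positive at Ct 44 has normalized Ct 44 − 3.83 = 40.17 and load 4.83/3.321928 = 1.45, against 0 for a negative. A floor at 0 for normalized positives is optional; it would truncate genuine low values and is not needed to resolve this point. If the existing code already exempts negatives, the sentence simply records that.

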# 6.10.1. Primary Outcome and Methodology

#### Treatment Arm 23

The primary objective is to assess PK in the pediatric PK population. The primary parameter for analysis is the AUC from 0 to infinity. Other parameters, such as half-life, apparent clearance, and apparent volume of distribution, may be reported. A comparison of pediatric exposures to adult exposures will be performed to demonstrate similarity between adults and pediatrics and confirm the pediatric dose.

# 6.10.2. Additional Analyses of the Primary Outcome

Not applicable for this cohort.

# 6.11. Bioanalytical and Pharmacokinetic/Pharmacodynamic Methods

Pharmacokinetic and PD analyses are the responsibility of the Eli Lilly and Company PK/PD group.

Bebtelovimab concentration data will be analyzed using a population PK approach via nonlinear mixed-effects modeling with the NONMEM software. In addition, the effects of participant factors, such as weight and age on PK parameters may be evaluated. If antidrug antibody is detected from immunogenicity testing, its impact on bebtelovimab PK may also be evaluated.

A limited number of pre-identified individuals may gain access to interim data prior to the primary lock, in order to initiate the population PK/PD model development processes.

Pharmacodynamic endpoints will be summarized using descriptive methodology. The SARS-CoV-2 viral dynamics will include evaluation of

change from baseline in SARS-CoV-2 viral load (Days 5, 7, and 11) AUC, and time to SARS-CoV-2 clearance.

Additional PK/PD concentration-response analysis may be performed PK/PD analyses on adolescents in the study will be treated as secondary to support the pediatric analyses.

# 6.12. Safety Analyses

Percentages will be calculated using the safety population as the denominator. For events that are sex-specific, the denominator and computation of the percentage will include only participants from the given sex.

# 6.12.1. Baseline and Postbaseline Definitions for Safety Groups

Table PYAB.6.7 provides conceptual definitions of baseline and postbaseline by analysis type. More specific detail for each submission is provided in an appendix, if necessary.

Table PYAB.6.7. Baseline and Postbaseline Definitions for Safety Groups Initial Controlled Periods of Individual Studies Controlled Integrated Analysis Sets

Analysis Type	Baseline	Postbaseline	
TEAEs	Start of screening and ends	Starts after initiation of the first dose and ends	
	prior to the first dose.	on or prior to the day of study disposition	
Treatment-Emergent	Start of screening and ends	Starts after initiation of the first dose and ends	
Abnormal Laboratory Values and Vital Signs	prior to the first dose.	on or prior to the day of study disposition.	
	All scheduled and unscheduled measurements will be included.	All scheduled and unscheduled measurements will be included.	
Change from Baseline to	Start of screening and ends	Starts after initiation of the first dose and ends	
Study Day xx and to Last	prior to the first dose.	on or prior to the day of study disposition.	
Postbaseline for Laboratory			
Values and Vital Signs	The last scheduled nonmissing	Only scheduled visits will be included. The	
	assessment recorded prior to	early termination visits are considered	
	the date of the first dose.	scheduled visits.	

Abbreviation: TEAE = treatment-emergent adverse event.

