COVID-19 Symptoms	X	X	X	X	X	X	X	X	X	X	X				Day 1: assess prior to dosing The presence of absence of symptoms are collected from the participants or their parents/legal guardian.
Laboratory Tests and Sample Collections															
Hematology		X		X				X		X	X				Day 1: before treatment administration All other days: sample may occur at any time during the day Lilly-designated central laboratory

	Period I Screening	Period II Treatment Period											Period III Post- Treatment Follow-Up		
Study Day from Treatment Assignment		1	2, 3, 4	5	6	7	8, 9, 10	11	22	29	ED	Follow-up if hospital inpatient on Day 29	60	85	
Visit interval tolerance (days)		—	—	±1	—	+1	—	±2	±2	±3	±2	Every 7 days until discharge or Day 60	±4	±4	
Visit Detail		O	T,I	O,H	T,I	O,H	T,I	O,H	T,I	O,H	O,H		O,H	T,I	O = Outpatient clinic, H = Home Visit, T = Telephone, I = IT-Assisted Virtual Visit
Clinical Chemistry		X		X				X		X	X				Day 1: before treatment administration All other days: sample may occur at any time during the day Lilly-designated central laboratory
Documentation of positive SARS-CoV-2 viral infection	X														Sample for first positive test must be collected within 3 days prior to start of treatment administration. Local laboratory and/or Point-of- Care testing.
PD swab		X		X		X		X		X	X				Swab is taken from both nostrils. Day 1: swab before treatment administration. Methods include nasopharyngeal (preferred) or mid-turbinate. The same method of sample collection must be used per participant for the duration of the study. Switching methods is not allowed. Lilly-designated central laboratory

	Period I Screening	Period II Treatment Period											Period III Post- Treatment Follow-Up		
Study Day from Treatment Assignment		1	2, 3, 4	5	6	7	8, 9, 10	11	22	29	ED	Follow-up if hospital inpatient on Day 29	60	85	
Visit interval tolerance (days)		—	—	±1	—	+1	—	±2	±2	±3	±2	Every 7 days until discharge or Day 60	±4	±4	
Visit Detail		O	T,I	O,H	T,I	O,H	T,I	O,H	T,I	O,H	O,H		O,H	T,I	O = Outpatient clinic, H = Home Visit, T = Telephone, I = IT-Assisted Virtual Visit
Serum or Urine pregnancy (local)	X														Pregnancy tests prior to the first dose of investigational product for females if 
 aged ≥10 years <10 years at investigator’s discretion menarche is reached or there is reason to believe that the patient is sexually active. Local laboratory

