# 6.1.2. Definition of Study Baseline

Unless otherwise specified, for efficacy and health outcome, baseline is defined as the last nonmissing assessment recorded on, or prior to, the date of the first study drug administration at study Day 1.

Baseline for safety analyses is described in the safety section.

Change from baseline will be calculated as the visit value of interest minus the baseline value. If a baseline values or the value at the visit is missing for a particular variable, then the change from baseline is defined as missing.

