Estimates of continuous efficacy, safety, and health outcome variables with a single postbaseline timepoint will be made using analysis of covariance (ANCOVA) with baseline value in the model. The LS mean, standard error, and 95% CI, unless otherwise specified, will also be reported. Missing data imputation method for the ANCOVA model is specified in Section 6.3.

Estimates of binary endpoints will be made using logistic regression. The model will include the weight range groups used for dosing, unless otherwise noted. The CIs of any rate estimates will be reported.

The Kaplan-Meier (KM) product limit method will be used for time-to-event analyses. Time for all analyses will be described in units of days.

For all change from baseline analyses, patients who do not have a valid baseline measure will be excluded.

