# 8. Appendices

# Appendix 1. NEWS2 Scoring Scale

The National Early Warning Score 2 (NEWS2) is based on a simple aggregate scoring system in which a score is allocated to physiological measurements, already recorded in routine practice, when participants present to, or are being monitored in hospital. Six simple physiological parameters form the basis of the scoring system:

□ respiration rate
 □ oxygen saturation
 □ systolic blood pressure (BP)
 □ pulse rate
 □ level of consciousness or new confusion, and
 □ temperature.

Physiological parameter	3	2	1	Score 0	1 1	2	3
Respiration rate (per minute)	≤8		9–11	12–20		21–24	≥25
SpO 2 Scale 1 (%)	≤91	92-93	94–95	≥96			
SpO 2 Scale 2 (%)	≤83	84–85	86–87	88–92 ≥93 on air	93–94 on oxygen	95–96 on oxygen	≥97 on oxygen
Air or oxygen?		Oxygen		Air			
Systolic blood pressure (mmHg)	≤90	91–100	101–110	111-219			≥220
Pulse (per minute)	≤40		41–50	51-90	91–110	111–130	≥131
Consciousness				Alert			CVPU
Temperature (*C)	≤35.0		35.1–36.0	36.1-38.0	38.1-39.0	≥39.1	

Abbreviations: CVPU =Confusion, Voice, Pain, Unresponsive; NEWS2 = National Early Warning Score 2; SpO2 = oxygen saturation.

Figure APP.1.1. NEWS2 scoring.

NEW score	Clinical risk
Aggregate score 0–4	Low
Red score Score of 3 in any individual parameter	Low-medium
Aggregate score 5–6	Medium
Aggregate score 7 or more	High

Abbreviation: NEWS2 = National Early Warning Score 2.

Figure APP.1.2. NEWS2 scoring clinical risk thresholds.

Consciousness is only collected for participants who are inpatients, therefore, if there is a missing scoring for consciousness then it will be imputed as 0 (Alert).

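### The safety change-from-baseline rule in SAP Table PYAB.6.7 cuts off at the dosing date, which excludes the only scheduled pre-dose laboratory sample (Day 1)

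*SAP*

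**What the plan says.** The Change from Baseline row of SAP Table PYAB.6.7 covers laboratory values and vital signs, and its baseline cell makes two statements. The baseline period starts at screening and ends "prior to the first dose". The value to be used is then given in a sentence that the table layout breaks into three pieces: "The last scheduled nonmissing", "assessment recorded prior to", "the date of the first dose".

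For hematology and clinical chemistry, the Arm 23 schedule (Protocol Addendum 2.2.1) gives the timing as "Day 1: before treatment administration All other days: sample may occur at any time during the day". Both rows are blank at Screening. Study drug is given on Day 1 only.

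SAP 6.1.2 deals with a missing baseline or visit value: "then the change from baseline is defined as missing". SAP 6.1.4 adds: "For all change from baseline analyses, patients who do not have a valid baseline measure will be excluded". For efficacy, 6.1.2 accepts values recorded on the dosing date, but it leaves the safety baseline to the safety section, which means this table.

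**The concern.** A cut-off at the dose and a cut-off at the dosing date give the same result only when a scheduled assessment exists on an earlier day. For laboratory tests in this arm there is none. The selection rule therefore discards the one sample that the schedule places before dosing to serve as baseline. The requirement that the value be scheduled also stops an earlier unscheduled sample from filling the gap.

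Two programmers working from the same cell could get opposite results. One following the date rule would have no laboratory change values at all; one following the period rule would have all of them. An analysis plan should not leave that to be settled during programming.

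**Working it through.** The documents state no count of participants with a laboratory baseline, so there is no planned figure to reproduce. The check is a count from the schedule.

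**Inputs**
- Scheduled visits by test and day of dosing: Protocol Addendum 2.2.1.
- Number of participants: about 50 aged 0 to 12 years, plus up to about 20 aged 12 to 17 and under 40 kg (SAP 5.3). The total is 50 + 20 = 70.
- Scheduled post-dose laboratory visits: Days 5, 11 and 29, so 3. Full attendance and no early-discontinuation visits are assumed.

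**Scheduled assessments that qualify as baseline**

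| Test | Scheduled at | Before the dosing date | Before the dose |
|---|---|---|---|
| Hematology | Days 1, 5, 11, 29, ED | none | Day 1 |
| Clinical chemistry | Days 1, 5, 11, 29, ED | none | Day 1 |
| Vital signs | Screening, Days 1, 5, 7, 11, 29, ED, 60 | Screening | Screening, Day 1 pre-dose |

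**Laboratory change values per analyte** = participants with a baseline × post-dose visits
- Date rule: 0 × 3 = 0, for either sample size.
- Period rule: 50 × 3 = 150, or 70 × 3 = 210.

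**Vital signs.** The date rule removes the reading taken just before dosing and leaves only a screening reading, provided screening fell on an earlier date. The schedule's note on screening vital signs says data are not entered on the CRF. It is unclear whether this covers SpO2 only or every screening vital sign, and the main protocol section that it refers to was not available. The loss of vital-sign baselines could therefore be anywhere from 0% to 100%.

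**Does anything else in the documents repair the rule?**
- SAP 6.12.1 calls its definitions conceptual and allows for detail in an appendix. The only appendix is "Appendix 1. NEWS2 Scoring Scale".
- SAP 6.12.6 on laboratory evaluation gives no baseline rule.
- The efficacy baseline in SAP 6.1.2 does not apply to safety.
- The addendum states that its sections replace the corresponding main-protocol sections, so a screening laboratory draw cannot be assumed from the main protocol.
- Table PYAB.6.9 asks for the last baseline in the vital-sign box plots and sets no date limit. It covers vital signs and physical characteristics, so it does not help the laboratory tests.

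**The case against.** The strongest reply is that this is template wording whose intent is clear. The table calls itself conceptual, the row label still contains a placeholder day, and the cell's opening statement agrees with the two rows above it. A programmer who found no laboratory baseline for anyone would notice on the first run and use the Day 1 sample. The second statement can also be read as narrowing the first rather than contradicting it.

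The affected output is also thinly specified. SAP 6.12.6 names no laboratory change table or model, and the protocol's list of secondary safety summaries contains none. The main laboratory safety signal, treatment-emergent abnormalities, uses a row that is not affected. The cohort is single-arm and descriptive, so no treatment comparison can be biased.

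Much of this stands. Zero laboratory results in the final report is unlikely, and it is right that the damage is confined to one row. But the expected rescue works only by departing from the written rule, which shows that the rule is wrong. Reading the second statement as a narrowing of the first does not help either, because the set of eligible laboratory values is still empty. The row names laboratory values explicitly, so an analysis is intended even though its display is not described. The vital-signs point is secondary, and Table PYAB.6.9 may simply mean the last value within the period that Table PYAB.6.7 defines.

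**Conclusion.** The concern holds and should be fixed. As written, the selection rule leaves 0 of about 50 participants (0 of about 70 with the adolescents) with a laboratory baseline for change. Under the period rule in the same cell, every participant with a Day 1 pre-dose sample has one. Per analyte that is 0 change values against up to 150 or 210, assuming full attendance at the three post-dose laboratory visits.

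For vital signs, the Day 1 pre-dose reading is lost as baseline for every participant, and the net loss cannot be determined from these documents.

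The PK primary endpoint is not affected. Nor are the adverse-event, serious adverse-event, interrupted-administration and hypersensitivity summaries, or the treatment-emergent laboratory and vital-sign abnormalities.

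**What to change.** In the Change from Baseline row of Table PYAB.6.7, replace the dosing-date cut-off with: before the start date and time of study drug administration, Day 1 pre-dose values included. This agrees with the cell's own first statement and with the rows above it.

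The cut-off should be a date and time. Borrowing the efficacy wording from SAP 6.1.2, which accepts anything on the dosing date, would also admit the vital-sign readings taken on Day 1 after dosing. SAP 6.1.2 itself needs no change for this point.

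The cost is one phrase in the SAP. The schedule already requires the Day 1 laboratory draw before administration and a vital-sign reading immediately before it, so no procedure or sample is added. The correction should be made before the safety programs are written, so that the choice of baseline is not made after the data are seen.
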